Estrogen has the potential to provide therapeutic advantages in managing irritative voiding symptoms, such as urgency, frequency, and urge urinary incontinence. The precise mechanism by which the medication induces the reversal of urogenital atrophy or its direct impact on the lower urinary tract remains uncertain. One challenge in comprehending the contradictory data now available on the subject pertains to the utilization of multiple estrogen formulations, varying dosages, diverse methods of administration, and the inconsistent use of concomitant progesterone. There exists substantial evidence supporting the efficacy of low-dose vaginal estrogen treatment in reversing urogenital atrophy, encompassing both the symptoms and cytological changes.^(20, 21)

Review literatures

- **Comparison: Vaginal estradiol 25 mcg versus placebo**

Research title	country	year	Dosage	F/U	Outcome Measurement	Results
Low-dose 17beta-estradiol vaginal tablets in the treatment of atrophic vaginitis: a double-blind placebo-controlled study ⁽¹⁴⁾	Denmark	Eriksen PS 1991	estradiol 25 mcg vs placebo	12 weeks	urological symptoms change	Vg E -> improve 62.8% placebo -> improve 32.4%
Local estrogen treatment in patients with urogenital symptoms ⁽²²⁾	Croatia	Simunic 2003	estradiol 25 mcg vs placebo	12 months	symptoms/signs of urinary atrophy Dysuria Frequency/nocturia Urinary tract infection Urinary incontinence Urinary atrophy	n=330->84 n=371->74 (Improve 80%) n=186->49 n=245->106 n=406->121
Vaginal estradiol for the treatment of lower urinary tract symptoms in postmenopausal women--a double-blind placebo-controlled study ⁽²³⁾	England	Cardozo 2001	estradiol 25 mcg vs placebo	12 weeks	N/A	A significantly greater reduction in the symptom of urinary urgency on visual analogue score was detected for women in stratum A (sensory urgency)

- **Weber MA et al. (2015)**

Local Estrogen for Pelvic Floor Disorders: A Systematic Review

Comparison: Vaginal estrogen versus placebo or no treatment

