The procedure commonly incorporates the utilization of Cybow™ 10-urinalysis test strip, which are advanced diagnostic tools designed to analyze multiple urine parameters simultaneously. Initially, a fresh clean-voided midstream urine sample is collected and visually inspected for its

color, clarity, and odor. Subsequently, the Cybow strip is immersed into the urine specimen for a specific duration, enabling the strip's chemical pads to react with the components in the urine. These pads, strategically embedded with reagents, undergo color changes in response to the presence and concentration of specific analytes, including but not limited to pH, protein, glucose, ketones, nitrites, leukocytes, bilirubin, and urobilinogen. The strip is then carefully removed and placed on a flat surface, allowing for accurate color comparison with standardized color charts to quantify the concentration of each parameter. For this research purpose, exclusion of urinary tract infection is imperative for eligible criteria.

Interpretation: In the event of leukocytes displaying a concentration of one plus (1+) or higher, or a positive nitrite result, these findings could be indicative of a urinary tract infection (UTI). It is imperative to note that the presence of a UTI serves as an exclusion criterion during the evaluation process.⁽³⁹⁾

7.6) Statistical analysis

Demographics for enrolled participants will be tabulated and described for each study group including age, ethnicity, occupation etc. All clinical and laboratory data related to objectives will be summarized and compared for each group. Appropriate statistics will be calculated to summarize and compare the range, means, medians, etc., and variability of numerical data. Confidence limits (95%) for means, geometric means and proportions will be calculated. Graphical summaries (e.g., box plots, histograms) will be used to describe and compare distributions of numeric variables. Frequency tables will be used to summarize distributions for discrete data. All clinical and laboratory data related to outcomes will be summarized and compared in the two regimens. T-tests and chi-square tests will be used to assess the statistical significance of differences in two means (possibly log-transformed) or proportions. Descriptive summaries of serious adverse events, subject discontinuations due to adverse events, and potentially clinically significant abnormal values (clinical laboratory or vital signs) will also be provided.

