7.7) Study Subjects

Collect data and publicizing invitations to participate in research “Efficacy of Vaginal 17 β -Estradiol on the Urinary Storage Symptoms in Postmenopausal Women: A Randomized Double-blind, Placebo-controlled Study” in Outpatient departments, Department of Obstetrics & Gynecology, Faculty of Medicine Ramathibodi Hospital

[figure not shown]
7.8) Research site

Outpatient departments, Department of Obstetrics & Gynecology, Faculty of Medicine
Ramathibodi Hospital

7.9) Research plan

Activities	2023					2024												2025		
	8	9	10	11	12	1	2	3	4	5	6	7	8	9	10	11	12	1	2	3
1. Literature review and proposal preparation	■	■	■																	
2. Proposal submission and approval			■	■	■															
3. Data collection and analysis								■	■	■	■	■	■							
4. Manuscript writing and submission																■	■	■	■	

8. Protocol Flow Chart

9. Sample size calculation and inclusion/exclusion criteria

- **Sample size calculation**

The sample size is calculated using two independent population proportions formula.

$$n_1 = \left[\frac{z_{1-\frac{\alpha}{2}} \sqrt{\bar{p}\bar{q} \left(1 + \frac{1}{r}\right)} + z_{1-\beta} \sqrt{p_1 q_1 + \frac{p_2 q_2}{r}}}{\Delta} \right]^2$$

$$\Delta = p_1 - p_2, \quad \bar{p} = \frac{p_1 + p_2 r}{1 + r}, \quad r = \frac{n_2}{n_1}$$

$$q_1 = 1 - p_1, \quad q_2 = 1 - p_2, \quad \bar{q} = 1 - \bar{p}$$

Proportion in group1 (p1) = 0.63

Proportion in group2 (p2) = 0.32

alpha(α) = 0.05 , Beta(β) = 0.2

According to Eriksen PS, Rasmussen H (1991)⁽¹⁴⁾ , after 12 weeks, 62.8% of the women with urological symptoms underwent a change for the better in the estradiol (Vagifem®) group compared to 32.4% in the placebo group. (P < 0.001). With sample size (n) equal to 39 subjects per group and add drop out at rate of 10%, which is equal to 43 subjects per group. The total number of sample size will be 86 subjects.

- **Inclusion criteria**

1. Presenting with storage phase symptom score more than/equal to 1 evaluated by the ICIQ-FLUTS questionnaire in these items

- Item 2a) nocturia and/or
- Item 3a) urgency and/or
- Item 5a) daytime frequency and/or
- Item 9a) UUI and/or
- Item 11a) SUI

2. Being natural or surgical menopause for more than 1 year

3. Absence of urinary tract infection or other identifiable cause

4. Not using hormone replacement therapy or any route of estrogen within 4 weeks

5. Never undergone onabotulinumtoxinA therapy, PTNS, or neuromodulation for OAB treatment

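### Section 9's own formula gives 40 per group, not 39, and its 10% dropout allowance leaves power at about 79% rather than 80%

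*Combined protocol and SAP*

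**What the plan says.** Section 9 (Sample size calculation) says that "The sample size is calculated using two independent population proportions formula" and prints that formula in the form with pooled variance under the null and unpooled variance under the alternative. The inputs are "Proportion in group1 (p1) = 0.63" and "Proportion in group2 (p2) = 0.32", with alpha 0.05 (two-sided, since the formula uses z at 1 − α/2) and beta 0.2. Section 7.4 gives 1:1 allocation.

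The result is "sample size (n) equal to 39 subjects per group and add drop out at rate of 10%, which is equal to 43 subjects" per group, and "The total number of sample size will be 86 subjects".

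The two proportions are rounded from a published placebo-controlled trial of the 25 mcg tablet, in which "62.8% of the women with urological symptoms underwent a change for the better" on estradiol, against 32.4% on placebo. The literature table in the background section gives the same pair of rates.

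For the analysis, section 7.6 says that "T-tests and chi-square tests will be used to assess the statistical significance of differences in two means" or in proportions. It defines no analysis set and no rule for missing outcomes.

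**The concern.** Two small slips in section 9 run in the same direction.

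- The formula result lies above 39, and a sample size has to be rounded up to meet its power target.
- The dropout allowance was added as a percentage of the evaluable number. Taking 10% away from 43 therefore does not return 39.

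Beta = 0.2 is the design input that justifies 86. Adding a dropout allowance implies that 80% power was meant to survive the dropout. Anyone who recomputes section 9 from its printed formula and inputs will get 40, and will find that the allowance does not quite protect the stated power. What is at stake is the accuracy of a stated design figure, not the viability of the trial.

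**Working it through.** **Inputs (section 9).** p1 = 0.63, p2 = 0.32, so Δ = 0.31; r = 1; z(0.975) = 1.960; z(0.80) = 0.8416; mean proportion p̄ = (0.63 + 0.32)/2 = 0.475.

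**Step 1. Evaluable number per group.**

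n = {[z(0.975) × √(2p̄q̄) + z(0.80) × √(p1q1 + p2q2)] / Δ}²

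- √(2 × 0.475 × 0.525) = 0.7062, times 1.960 = 1.3842
- √(0.63 × 0.37 + 0.32 × 0.68) = 0.6713, times 0.8416 = 0.5650
- n = (1.9492 / 0.31)² = 39.54, so **40** when rounded up

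With hand-rounded z values of 1.96 and 0.84 the formula gives 39.49. The nearest integer is 39, which is a plausible origin of the stated figure. It still rounds up to 40.

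**Step 2. Dropout allowance.**

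- 39 × 1.10 = 42.9, which reproduces the plan's 43
- 43 × 0.90 = 38.7 expected evaluable per group
- 39 / 0.90 = 43.3, so 44 would be needed even to keep 39
- Largest dropout at which 43 per group still holds 80% by the formula: 1 − 39.54/43 = 8.1%, below the plan's own 10%

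**Step 3. Power by the same formula.** Power = Φ{[Δ√n − z(0.975)√(2p̄q̄)] / √(p1q1 + p2q2)}. At n = 38.7 this is Φ[(0.31 × 6.221 − 1.3842)/0.6713] = Φ(0.811) = 79.1%.

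| Evaluable per group | 0.63 vs 0.32 | 0.628 vs 0.324 |
|---|---|---|
| 38.7 (43 less 10%) | 79.1% | 77.4% |
| 39 | 79.4% | 77.8% |
| 43 (no dropout) | 83.3% | 81.7% |

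**Step 4. Exact check.** These are exact binomial powers of the uncorrected Pearson chi-square test. The last row averages over independent Binomial(43, 0.9) completers in each arm.

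| Evaluable per group | 0.63 vs 0.32 | 0.628 vs 0.324 |
|---|---|---|
| 38 and 38 | 78.8% | 77.1% |
| 39 and 38 | 77.9% | 76.1% |
| 39 and 39 | 80.5% | 78.9% |
| 43 and 43 | 82.7% | 81.1% |
| 43 enrolled, 10% random dropout | 79.5% | 77.8% |

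At 10% dropout an arm keeps fewer than 39 of its 43 with probability 43%. Both arms keep at least 39 with probability 32%.

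**Step 5. Sensitivity to rounding the rates.** Rounding widens the difference from 30.4 to 31 percentage points. At 0.628 vs 0.324 the formula gives 41.17, so 42 per group, and 43 per group holds 80% only up to 1 − 41.17/43 = 4.3% dropout.

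**Step 6. Smallest enrolment that keeps 80% after 10% dropout.**

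- Declared rates: 44 per group (88 in total), 39.6 evaluable, 80.1% by formula, 80.4% exact averaged
- Source rates: 46 per group (92 in total), 41.4 evaluable, 80.2% by formula, 80.6% exact averaged

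**The case against.** The strongest reply is that this is rounding noise. The stated 39 is within one of the formula, section 9 gives no rounding rule, and the gap is smaller than the error of the normal approximation. Exact chi-square power moves in steps: at the declared rates it is 80.5% at 39 per group, 85.0% at 42 and 82.7% at 43. By the exact test, 39 per group does reach 80%. This stands, and it is why the point is minor. It does not remove the shortfall, because 39 in both arms is not what 10% dropout from 43 usually leaves. Averaged over dropout, the exact figure is still 79.5%.

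A second reply is that section 9 gives beta only as an input and never claims 80% after dropout, and that section 7.6 does not say dropouts are left out of the analysis. This is fair. If all 86 were analysed, the no-dropout powers apply and only the 39-versus-40 discrepancy remains. Still, an allowance for dropout has no purpose unless dropouts are expected to be lost to the analysis.

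A third is that 44 per group, with 39.6 evaluable, seems at odds with a requirement of 40. The two answer different questions. Forty is the smallest whole number of evaluable women that meets the target. Forty-four is the smallest enrolment whose expected evaluable number exceeds 39.54. Insisting on 40 evaluable would give 40/0.9 = 44.4, so 45 per group (90 in total).

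Finally, the source rates come from a trial of the 25 mcg tablet in atrophic vaginitis, so fractions of a point on them should not be over-read. That is right, and those figures serve only as sensitivity.

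**Conclusion.** The point holds as a minor arithmetic error. On its declared inputs the formula in section 9 requires 40 evaluable per group, not 39. Enrolling 43 per group with 10% dropout gives about 79% power (79.1% by formula, 79.5% exact averaged), which is 0.9 or 0.5 points below the 80% implied by beta = 0.2. At the unrounded source rates it is about 77–78%.

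The power figures rest on two assumptions: that dropouts leave the analysis, and that the exact averages may treat dropout as independent and equal in the two arms. The 39-versus-40 discrepancy needs neither. With no dropout, 43 per group exceeds 80% on either pair of rates, so this is not an underpowered design.

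**What to change.** Keep 86 and restate the result in section 9, for example:

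> The formula gives 40 evaluable participants per group. Enrolling 43 per group (86 in total) leaves about 38.7 evaluable per group after 10% dropout. This gives about 79% power at 63% vs 32%, and about 77% at the unrounded source rates of 62.8% vs 32.4% (two-sided alpha 0.05).

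The cost is one reworded statement. Enrolment, procedures and analysis are unchanged; the plan would report about 79% after dropout in place of the implied 80%. If the sponsor preferred to hold 80% after 10% dropout, the minimum would be 44 per group on the declared rates or 46 at the source rates, but an error of this size does not call for that.

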4. Not using hormone replacement therapy or any route of estrogen within 4 weeks
5. Never undergone onabotulinumtoxinA therapy, PTNS, or neuromodulation for OAB treatment
6. Willing to adhere to the research protocol and actively participate in the scheduled follow-up appointments as delineated within the framework of this study

Exclusion criteria

1. Contraindication for estrogen therapy: undiagnosed abnormal vaginal bleeding, previous thromboembolic event, breast cancer, gynecologic/genitourinary malignancy, active liver disease
2. Pelvic organ prolapse of anterior compartment stage III and IV
3. Immunocompromised patient or taking immunosuppressant drug
4. History of antibiotics drug use within the past 7 days
5. History of bladder outlet obstruction
6. History of using anti-muscarinics, β 3-adrenoceptor agonists, vaginal energy-based devices (laser and radiofrequency) or electromagnetic energy-based therapies within the past 2 weeks
7. History of documented positive urine culture in the past 6 weeks
8. Have an allergic reaction to study's drug
9. Any other significant finding that in the opinion of the investigator would increase the risk of having an adverse outcome from participating in this study

Women who meet inclusion criteria will be randomized with block randomization technique and a ratio of treatments of 1:1. The sequence generation will be performed under supervision of a senior statistician at the section of Clinical Epidemiology and Biostatistics in Ramathibodi Hospital.

The random sequences will be generated using Stata version 18. This is an automated process with no interfere from the investigators.

Upon a subject's successful enrollment in the clinical trial following eligibility assessment, principal investigator or research personnel shall provide participants with a comprehensive Thai guidebook for behavior modification which is designed to ensure the harmonization of knowledge and behaviors among all trial participants. This guidebook was developed and published by IUGA and will be distributed by research assistants.

Trial Treatment: Dosage Form, Regimen, Route of Administration

- **17 β -Estradiol 10 mcg** (Femiest® Haupt Pharma Munster GMBH, Muenster, Germany
(ESTRADIOL HEMIHYDRATE 0.0103 milligram, pH 6.94)

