17 β -Estradiol will be administered to group A treatment arm intravaginally. The assigned dosage will be one vaginal tablet daily for two weeks then one vaginal tablet twice a week for 10 weeks. Participants will be carefully monitored for any changes in clinical condition in each follow-up visits using logbook. It is important to clarify that we are not using 17 β -Estradiol (Vagifem®) 25 mcg as the study drug. Although 17 β -Estradiol 25 mcg is frequently mentioned in literature reviews and has been historically used for treating vaginal dryness, this drug is currently not available in Thailand. Therefore, we are using 17 β -Estradiol (Femiest®) 10 mcg as an alternative for our study drug. Notably, 17 β -Estradiol 10 mcg has been shown to provide a therapeutic dose equivalent to that of 17 β -Estradiol 25 mcg for treatment, as stated by the FDA. This decision ensures that participants receive an effective and appropriate dosage while adhering to the availability of medications in our region.

- **Placebo**

Placebo will be administered to group B treatment arms intravaginally. The assigned dosage will be one vaginal tablet daily for two weeks then one vaginal tablet twice a week for 10 weeks. Participants will be carefully monitored for any changes in clinical condition in each follow-up visits. Placebo is produced by Chulalongkorn University Drug and Health Products Innovation & Promotion Center, Faculty of Pharmaceutical Sciences, Chulalongkorn University. Details for presentation and packing are as follows;

Appearance	White, round, biconvex with "E" imprint one side
Weight	106 - 110 mg
Hardness	4.1 - 4.8 kP

Thickness	3.26 - 3.3 mm
Diameter	6.02 - 6.03 mm
Disintegration time	4 min 58sec - 7min 42sec
pH	7.18
Placebo contains	
 1. Agglomerated Lactose 2. Microcrystalline cellulose PH 102 3. Magnesium stearate

Both subject groups will be counseled on potential signs/symptoms of adverse events and post-marketing experience, such as breast pain, peripheral edema, and postmenopausal bleedings. Due to the vaginal administration and minimal systemic absorption, it is unlikely that any clinically relevant drug interactions will occur with 17 β -Estradiol. However, interactions with other locally applied vaginal treatments will be considered and advised to the patients. If a dose is forgotten, participants will be advised that it should be taken as soon as he/she remembers. A double dose should be avoided.

Random allocation

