
Each participant in the study will receive a prescription for the research drug, an adequate supply to cover a 12-week treatment duration. This drug will be uniformly packaged within identical containers, featuring a unique alphanumeric code and detailed usage instructions on the label, thereby avoiding the inclusion of the original medication name. The data analysis will be performed by a statistician who will be the sole individual privy to the allocation of drug A or drug B to their respective groups. It is essential to note that the statistician will remain unaware of which of the two is the active drug and which is the placebo. Additionally, an independent statistician will maintain a sealed randomization list as a contingency. Allocation will be as follows;

Group A

17 β -Estradiol 10 mcg (Femiest® Haupt Pharma Munster GMBH, Muenster, Germany
(ESTRADIOL HEMIHYDRATE 0.0103 milligram)

Group B

Placebo

III. Third Visit

At four weeks after 2nd visit, the following study procedure will be performed;

- Bladder diary, the participant will be reminded to provide a three-day diary prior to schedule visit date.
- ICIQ-FLUTS
- ICIQ-LUTSqol
- PGI-I
- Vaginal pH
- Urethral maturation index (UMI)

Participants will also have clinical evaluation and vital signs measurements evaluated.

Compensation for participants will be provided.

IV. Fourth and Final Visit

At eight weeks after 3rd visit, the following study procedure will be performed;

- Pelvic exam
- Pelvic floor muscle strength measured as Brink scale
- Bladder diary, the participant will be reminded to provide a three-day diary prior to schedule visit date.
- ICIQ-FLUTS
- ICIQ-LUTSqol
- PGI-I
- Vaginal pH
- Urethral maturation index (UMI)

Participants will also have clinical evaluation and vital signs measurements evaluated.

Compensation for participants will be provided. Overall study procedures and flow diagram for study are outlined in topic No.8 Protocol flow chart.

7.5) Sample Preparation, Processing, Handling, Storage

- **Vaginal pH**

To assess pH, a piece of litmus paper (MQuant® pH-indicator stripe) will be placed on the lateral vaginal wall until moistened. A pH of 4.6 or greater indicates vulvovaginal atrophy

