6. Willing to adhere to the research protocol and actively participate in the scheduled follow-up

appointments as delineated within the framework of this study

- **Exclusion criteria**

1. Contraindication for estrogen therapy: undiagnosed abnormal vaginal bleeding, previous thromboembolic event, breast cancer, gynecologic/genitourinary malignancy, active liver disease
2. Pelvic organ prolapse of anterior compartment stage III and IV
3. Immunocompromised patient or taking immunosuppressant drug
4. History of antibiotics drug use within the past 7 days
5. History of bladder outlet obstruction
6. History of using anti-muscarinics, β 3-adrenoceptor agonists, vaginal energy-based devices (laser and radiofrequency) or electromagnetic energy-based therapies within the past 2 weeks
7. History of documented positive urine culture in the past 6 weeks
8. Have an allergic reaction to study's drug
9. Any other significant finding that in the opinion of the investigator would increase the risk of having an adverse outcome from participating in this study

10. Duration of data collection

It will take about 12 months for data collection, analyses and manuscript writing. All steps will start after the IRB ethical approval. If the research continues beyond the specified time or Ethics committee License expired, the investigators will request for renewal every year.

11. Risk of the study

There will be no physical, psychological or legal risks related to this study. Estradiol 10 mcg has a low dose and is safe. The adverse events observed with a higher frequency in patients treated with Estradiol 10 micrograms as compared to placebo and which are possibly related to treatment are presented as follows.⁽⁴⁰⁾

stem organ class	Common $\geq 1/100$ to $< 1/10$	Uncommon $\geq 1/1,000$ to $< 1/100$	Rare $\geq 1/10,000$ to $< 1/1,000$
Infections and infestation		Vulvovaginal mycotic infection	
Nervous system disorders	Headache		
Gastrointestinal disorders	Abdominal pain	Nausea	
Reproductive system and breast disorders	Vaginal haemorrhage, vaginal discharge or vaginal discomfort		
Skin and subcutaneous tissue disorders		Rash	
Investigations		Weight increased	
Vascular disorders		Hot flush Hypertension	

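### Section 11 states that the study carries no physical risk, but its own adverse-event table and its text on urethral sampling say otherwise

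*Combined protocol and SAP*

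**What the plan says.** Section 11 (Risk of the study) opens with "There will be no physical, psychological or legal risks related to this study" and continues with "Estradiol 10 mcg has a low dose and is safe". It then introduces a table of "The adverse events observed with a higher frequency in patients treated with Estradiol 10 micrograms as compared to placebo" that are also described as possibly related to treatment. The Common column (at least 1/100, below 1/10) holds headache, abdominal pain and the entry "Vaginal haemorrhage, vaginal discharge or vaginal discomfort". The Uncommon column includes nausea, rash, hot flush and hypertension. Later in the same section, the distal urethral swab, taken at visits 2, 3 and 4, is said to be capable of causing mild discomfort.

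On bleeding, exclusion criterion 1 (sections 7.4 and 9) begins "Contraindication for estrogen therapy: undiagnosed abnormal vaginal bleeding, previous thromboembolic event, breast cancer". Under Trial Treatment in section 7.4, both groups are to be counselled on "potential signs/symptoms of adverse events and post-marketing experience, such as breast pain, peripheral edema, and postmenopausal bleedings". Under Random allocation, each participant receives "an adequate supply to cover a 12-week treatment duration". The on-treatment visits come four weeks after visit 2 and eight weeks after that.

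**The concern.** A protocol's risk section is what an ethics committee relies on and what the consent discussion should reflect. Here its first sentence denies any physical risk, and the text that follows documents physical risks attributed to the study drug and a minor one from a study procedure. If the sentence is carried into the information sheet or a summary without the table, participants would be told something that the protocol itself contradicts.

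A related but smaller matter is that the protocol treats undiagnosed abnormal vaginal bleeding as important enough to bar entry and anticipates bleeding on treatment, yet the visible text does not connect the two. Site staff have no stated rule for an exclusion 1 condition that first appears after randomisation. Decisions on study tablets and on week-12 follow-up could then be made differently from one participant to the next.

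**Working it through.** **Step 1: the passages side by side.**

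| Place | What it implies about physical risk |
|---|---|
| Section 11, first sentence | None |
| Section 11, table, Common column | Haemorrhage, discharge or discomfort; headache; abdominal pain; each more frequent than on placebo and possibly related |
| Section 11, urethral sampling | Mild discomfort possible |
| Section 7.4, Informed Consent | Risks are to be discussed extensively |
| Section 13, Beneficence | Fewer side effects than other drugs, hence some |
| Section 14 | Free care for research-related injury, so injury is contemplated |

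The first row cannot be true together with the second and third. The last three rows also presuppose some risk. The sentence that the 10 mcg dose is safe is a judgement, and it could stand if qualified. The no-risk sentence is absolute and cannot.

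**Step 2: arm size.** Section 9 states 39 per group, 10% dropout and 43 per group. 39 × 1.10 = 42.9, which rounds to the stated 43 (86 in total). The point does not depend on the sample size. The arm size is needed only for scale.

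**Step 3: expected number with haemorrhage on estradiol.** Inputs are n = 43 and a rate p from the Common band, 0.01 to below 0.10. Expected number = n × p.

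- Lower end: 43 × 0.01 = 0.43
- Upper limit, not reached because the band is below 1/10: 43 × 0.10 = 4.3

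Chance of at least one case = 1 − (1 − p)^43.

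- Lower end: 1 − 0.99^43 = 0.351
- Upper limit, not reached: 1 − 0.90^43 = 0.989

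With the 39 women expected to complete, the expected number is 0.39 to just under 3.9.

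These figures are for haemorrhage alone, not for the whole table entry, which joins three terms. They assume that the band applies to each term separately, to this population and to 12 weeks of treatment. Section 11 gives no exposure period for the band.

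**Step 4: contact during treatment.** Visits fall at week 4 and week 4 + 8 = 12. The regimen is one tablet daily for 2 weeks, then twice weekly for 10 weeks: 14 + 2 × 10 = 34 tablets. By the week-4 visit, 14 + 2 × 2 = 18 of the 34 are scheduled. Clinical evaluation and vital signs are listed at both visits, and the pelvic examination is listed again only at the final one. The visible text gives no reporting instruction between visits and no rule for an exclusion 1 condition arising after randomisation.

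**The case against.** The strongest defence is that the risk is disclosed. The table sits directly under the sentence, so a committee reads both, and section 7.4 promises an extensive discussion of risks at consent. That limits the harm but does not make the sentence true. Because the consent pages are not available here, it would be wrong to infer that participants were misinformed.

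Four stronger readings are tempting, and the documents do not support them.

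- **That the plan has a bleeding participant continue tablets unassessed until the next visit.** No passage says so. Section 7.6 foresees discontinuations due to adverse events. Section 14 provides care for research-related injury or serious events on an emergency or routine basis, without tying it to scheduled visits. Section 7.4 adds monitoring and clinical evaluation at both visits. Silence on a rule is not an instruction to continue.
- **That a woman who starts bleeding necessarily meets the contraindication.** The criterion concerns undiagnosed abnormal bleeding. Whether new bleeding on a drug with bleeding as a listed reaction counts as undiagnosed is a clinical judgement that the protocol does not make.
- **That exclusion 1 contradicts the treatment section.** An entry criterion can coexist with bleeding as an expected reaction. What is missing is a link between them.
- **That the counselling list and the section 11 table must match.** The counselling list is given by way of example, also covers post-marketing experience, and already applies to both groups.

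The section 8 flow chart is also not visible, so the account of contacts rests on the text alone. What remains after these objections is the false sentence and one unstated rule.

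**Conclusion.** The main point holds: section 11's denial of physical risk is contradicted by its own table and by its own text on urethral sampling. This rests on the protocol's wording alone and needs no calculation.

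The scale is modest and imprecise: about 0.4 to just under 4.3 women with haemorrhage among 43 on estradiol, and a 35% to just under 99% chance of at least one, under the assumptions in step 3. The range is too wide to say more than that a case is plausible.

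The handling of exclusion 1 conditions during treatment is a secondary clarification. It is a missing detail for the sponsor to settle, not a demonstrated contradiction. Neither matter alters the primary outcome or the sample size.

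**What to change.** 1. Replace the no-risk sentence in section 11 with one that agrees with the adverse-event table and with the discomfort described for urethral sampling, and qualify the adjoining statement on safety to match.
2. Check that the participant information sheet does not repeat the no-risk sentence, and correct it if it does.
3. Reconcile exclusion 1 with the treatment and visit text in section 7.4. State whether the exclusion 1 conditions are meant to apply after randomisation, how such a condition is reported between scheduled visits, and how study tablets and week-12 follow-up are then handled. The clinical rule is for the sponsor to set, and none is proposed here. If the section 8 flow chart already covers this, a cross-reference is enough.

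The cost is protocol wording and, where needed, information-sheet wording. Depending on the rule chosen in item 3, there may be a few unscheduled contacts. No change to the design, sample size or analysis is needed.
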